5. STUDY STATISTICS

a. *Primary outcome variable.*

The primary outcome parameter is safety, patient tolerability, and patient satisfaction with the hand-held penile vibratory system.

b. *Secondary outcome variables.*

The secondary outcome parameter is erectile response (erection, rigidity, orgasm) and subjective patient and/or partner sexual satisfaction, when applicable.

c. *Statistical plan including sample size justification and interim data analysis.*

This is a prospective study. Descriptive statistics will be performed based on pre-treatment and post-treatment responses to validated sexual function questionnaires. This data will be utilized to perform power analyses to generate future studies. We will recruit a total of **20 patients** for this study.

d. *Early stopping rules.*

Patients who stop the use of the Viberec early, will be recorded and their reasoning will be documented. Since this is a phase I trial, patient safety and satisfaction is the primary outcome and therefore it will be essential to understand why a patient stops use prematurely.

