COVER PAGE

NCT number: 01715571

Official Title: Assessment of Penile Vibratory Stimulation
Using the Viberect in Men with Mild-Moderate ED

Document date: 5/7/2021

Principal Investigator: [name]

Participating Site: Johns Hopkins University, Baltimore,
MD, USA

Statistical Analysis Plan (SAP)

This was a pilot study and there were no data to suggest the magnitude of the effect of Viberect on ED, we performed power calculations for various scenarios of change in IIEF. The scenarios used a pattern of means with an absolute increase from pre-treatment to 4 weeks of 4 units for IIEF, and plausible conservative (higher than expected) values for the within-subject standard deviation that were increased until power fell below 80%. For IIEF, we evaluated power if the pre-treatment mean was the midpoint of the range of values eligible for study: IIEF = 18 (range 11-25). However, the power was not sensitive to the pre-treatment mean, and showed little variation according to the specific changes in mean score between time points, for a fixed overall change from pre-treatment to 4 weeks. The table below shows power to detect a 4 unit increase in IIEF with 20 patients evaluated at 4 time points, $\alpha = 0.05$, within-subject standard deviation and autocorrelation both constant over time. Power calculations were performed using PASS v. 11 (NCSS Software, Inc., Kaysville, UT), according to the method of Mueller (Mueller 1989).

Pattern of means over 4 time points		Within-subject SD	Power
Pre-test	4 weeks		
IIEF			
18	20	2	>0.99
18	20	3.5	0.88
18	20	3.8	0.81

Thus, despite the small size of the study, power is likely to be more than adequate to detect the minimum changes in IIEF (increase 4 units) considered clinically relevant.

Should a measurable positive effect be noted, a more extensive randomized, placebo controlled, blinded and possibly multi-institutional trial be considered. The information obtained from the pilot study a help guide future studies if appropriate.

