Pre-treatment IIEF, EHS, EDITS, and TSS scores was planning to be compared to post-treatment scores at 4 weeks. The primary analysis for all scores were repeated measures analysis of variance (RM ANOVA); if there are no missing time points, otherwise, a mixed model was used. The primary endpoint was the TIME effect, i.e. to test for a change from pre-treatment value of IIEF, EHS, EDITS, or TSS. The minimum change considered clinically relevant was an increase in IIEF and EDITS of 4 units and EDITS of 4 units. In addition to absolute change in IIEF or EDITS scores, we evaluated models of percentage change from pre-treatment value. If the overall effect of TIME is statistically significant, we used paired t-tests comparing pre-treatment to

each of the post-treatment values, with a Bonferroni p-value adjustment, to determine the time at which an increase in IIEF and EDITS of at least 4 points can first be detected. Covariates to be evaluated as potential confounding factors include age, comorbidity or cause of ED, body mass index, and other medications.

Data were analyzed using GraphPad Prism ver. 8 (GraphPad Software, San Diego, CA, USA). A P value $<.05$ was considered statistically significant.

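### The SAP's primary endpoint is change in four questionnaire scores, while the protocol's is safety, tolerability and device satisfaction; safety and tolerability have no specified analysis

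*SAP*

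**What the plan says.** **Protocol, section 5 (Study Statistics).** 5a: "The primary outcome parameter is safety, patient tolerability, and patient satisfaction with the hand-held penile vibratory system". 5b: "The secondary outcome parameter is erectile response (erection, rigidity, orgasm"). The 5b sentence goes on to add the subjective sexual satisfaction of the patient and/or partner, where applicable. 5d repeats that "patient safety and satisfaction is the primary outcome". The planned statistics in 5c are: "Descriptive statistics will be performed based on pre-treatment and post-treatment responses to validated sexual function questionnaires". No scale is assigned to any outcome in 5a or 5b.

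**Protocol, safety provisions elsewhere.** Section 2 has the diaries evaluated for safety. Section 2b adds a penile examination at week 4 and defines treatment failure as being unable to use the device as the trial recommends, either for mechanical reasons or because the sensation is not tolerated. 5d says: "Patients who stop the use of the Viberec early, will be recorded and their reasoning will be documented". Section 6 defines adverse events, sets weekly reporting to the investigators, provides for narratives of serious events and individual investigation of each adverse effect, and halts enrolment after a serious one.

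**SAP.** On power: "we performed power calculations for various scenarios of change in IIEF". On the endpoint: "The primary endpoint was the TIME effect, i.e. to test for a change from pre-treatment value of IIEF, EHS, EDITS, or TSS". The primary analysis for all four scores is repeated-measures ANOVA, or a mixed model if time points are missing. Adverse events, examination findings, treatment failure, early stopping and diaries are not mentioned.

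**The concern.** A trial should have one primary outcome hierarchy, and the analysis plan should implement it. Here the SAP replaces the protocol's hierarchy without saying so.

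Two things follow if the SAP is carried out as written. First, it produces no proportion of men with an adverse event and no proportion unable to use or tolerate the device. Serious events would be described in narratives with no stated denominator. Second, a significant change in IIEF or EHS in an unblinded, single-arm study could be reported as meeting the primary endpoint, although the protocol places erectile response second.

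**Working it through.** **1. The plan's own figure.** The only quantitative planning result is the SAP's power table. It has 3 rows, all for IIEF: power >0.99, 0.88 and 0.81 at within-subject SD 2, 3.5 and 3.8.

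Inputs from the SAP are n = 20, k = 4 time points, α = 0.05 and a 4-unit rise. The autocorrelation ρ is not given; I assume ρ = 0. I also assume a linear rise: 18, 19.33, 20.67, 22.

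- Sum of squared deviations from the mean of 20: 4 + 0.444 + 0.444 + 4 = 8.889.
- Noncentrality λ = n × SS / [SD² × (1 − ρ)] = 177.8 / SD², which is 44.4, 14.5 and 12.3.
- Noncentral F with 3 and 57 degrees of freedom: power 0.9999, 0.885 and 0.823.

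That agrees with the table to within 2 percentage points. The figure concerns IIEF only and says nothing about safety or tolerability. (The table prints a week-4 mean of 20, which does not match the 4-unit rise in the text. That is a separate matter.)

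**2. The two hierarchies side by side.**

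| Outcome | Protocol status | SAP status | Summary specified in SAP or 5c? |
|---|---|---|---|
| Safety | Primary (5a, 5d) | Not mentioned | No |
| Tolerability | Primary (5a) | Not mentioned | No |
| Satisfaction with the device | Primary (5a, 5d), no scale named | Primary, if measured by EDITS and TSS | Yes |
| Erectile response | Secondary (5b), no scale named | Primary, if measured by IIEF and EHS | Yes |
| Sexual satisfaction, patient or partner | Secondary (5b), no scale named | Not identified | No scale assigned |

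The scale assignments are inferences. Protocol section 2 describes the IIEF-5 as an erectile function component, and EHS is an erection hardness scale, close to the rigidity listed in 5b. EDITS and TSS are treatment satisfaction scales by name.

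**3. Count.** Of the 3 primary components in the protocol, 2 have no specified analysis. Of the 4 scales given primary status in the SAP, 2 belong by inference to a secondary outcome.

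**4. What a safety summary could show with 20 men.** This describes the sample size under any plan; it is not the size of the defect. Exact (Clopper-Pearson) 95% intervals:

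| Men with event | Proportion | 95% interval |
|---|---|---|
| 0/20 | 0% | 0 to 16.8% |
| 1/20 | 5% | 0.1 to 24.9% |
| 2/20 | 10% | 1.2 to 31.7% |
| 3/20 | 15% | 3.2 to 37.9% |

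For 0/20 the upper limit is 1 − 0.025^(1/20) = 0.168. For a 95% chance of seeing at least one event, 1 − (1 − p)^20 = 0.95 gives p = 1 − 0.05^(1/20) = 13.9% per man.

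**The case against.** The best defence is that safety is handled in the protocol, through diaries, examination, weekly reporting, narratives, individual investigation and recorded stopping reasons. In a single-arm study of 20 men, counts follow easily from such records. The study is a self-described pilot of an FDA-cleared device, and powering it on IIEF is weak evidence that IIEF was meant to outrank safety.

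Much of this stands, and it limits the point. A reader might infer that the trial neglects safety; the documents do not support that. What is missing is a specified summary, not safety monitoring. But collection, oversight and case narratives state no count, denominator or analysis set, and 5c confines its descriptive statistics to questionnaires. A plan detailed enough to include ANOVA, mixed models and Bonferroni-adjusted t-tests can carry two proportions for the protocol's lead outcomes.

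A reader might also infer that all four SAP scales are misplaced. EDITS and TSS plausibly serve satisfaction with the device, so the mismatch is partial. Whether change from a baseline taken before the device is supplied measures satisfaction with this device is a separate question, not judged here.

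Finally, the SAP is dated 2021 and reports that "Data were analyzed using GraphPad Prism ver. 8". A reader might infer that the endpoint was switched after results were seen. The documents do not show when or why the endpoint was set, so that cannot be concluded.

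**Conclusion.** The point holds as a conflict of text. The protocol and SAP name different primary endpoints, 2 of the protocol's 3 primary components have no specified analysis, and IIEF and EHS carry a primary status that 5a does not give them. Placing IIEF and EHS under 5b rests on what they measure, since 5b names no scale. Even without that inference, neither scale measures safety, tolerability or satisfaction with the device.

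Two stronger readings should be avoided. The wide intervals at n = 20 are not the measure of this defect. Nor would safety and tolerability summaries added now be wholly post hoc: the outcomes, the adverse event definition and the treatment failure definition are all in the protocol. Only the form of summary, and the use of treatment failure for tolerability, would be new.

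**What to change.** Align the SAP with protocol 5a and 5b.

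- **Primary, descriptive, over all men given a device:** (a) number and proportion with any device-related adverse event as defined in protocol section 6a, with serious events shown separately; (b) number and proportion with treatment failure as defined in section 2b, split into mechanical issues and inability to tolerate, with a table of early stops and reasons. Treatment failure is proposed as the nearest defined tolerability measure; the protocol does not call it that. Give exact 95% intervals so that a low count is not over-read.
- **Device malfunction:** state how it is counted. It appears in the adverse event definition and among potential serious events (section 6a), and mechanical issues appear under treatment failure (section 2b). These passages must be reconciled.
- **Scales:** label IIEF and EHS change as secondary. State which scale serves satisfaction with the device (primary) and which serves sexual satisfaction (secondary). EDITS and TSS are the likely choice for the former, but the protocol does not assign them.
- **If the data are already analysed:** report safety and tolerability as the protocol's prespecified primary outcomes, say that only the form of summary was chosen afterwards, disclose the mismatch, and do not present the IIEF or EHS result as the trial's primary finding.

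The cost is SAP rewording, two proportions, one table and a disclosure sentence, using the adverse event, examination and stopping records the protocol calls for. Complete per-man adverse event records cannot be taken for granted: the diary entries listed in section 2 do not include discomfort or malfunction, and the week-4 examination looks only at the penis. If records are incomplete, the report should say so. The downside is a primary safety result with a wide interval.

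### The SAP's primary endpoint covers four scores, each tested at .05 with no lead score and no adjustment across scores, so the chance of at least one false positive is roughly 10% to 18.5%, not 5%

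*SAP*

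**What the plan says.** The SAP's analysis paragraphs, which follow the power calculation, give every questionnaire the same standing: "The primary analysis for all scores were repeated measures analysis of variance (RM ANOVA"), replaced by a mixed model if time points are missing. The quantity tested is the effect of TIME, and the definition of the endpoint singles out no score: "i.e. to test for a change from pre-treatment value of IIEF, EHS, EDITS, or TSS". The threshold is stated once: "A P value $<.05$ was considered statistically significant".

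The one multiplicity rule comes after that test. Once TIME is significant for a score, follow-up paired t-tests set the baseline against "each of the post-treatment values, with a Bonferroni p-value adjustment". Their purpose is to locate when a rise of 4 points or more on IIEF and EDITS first appears. Percentage-change models for IIEF or EDITS are added with no alpha assigned.

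The SAP's power calculation covers IIEF only: 20 patients, four time points, alpha 0.05, and power of >0.99, 0.88 and 0.81 at within-subject SDs of 2, 3.5 and 3.8.

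Protocol section 5 differs. Items a and b make safety, tolerability and satisfaction primary and erectile response secondary. Item c plans no test: "Descriptive statistics will be performed based on pre-treatment and post-treatment responses to validated sexual function questionnaires". Protocol section 2 schedules the questionnaires at baseline and week 4 only.

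**The concern.** Four tests share the label of primary endpoint, and each may be called significant at .05. Nothing fixed in advance says which score leads or how to read one significant result among four. A reader of the results therefore cannot take a P value below .05 on one score as carrying a 5% error rate.

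This matters more here than the pilot label suggests. The study is single-arm and unblinded, has 20 men, and relies on self-reported scores. With no ranking in the plan, the emphasis can settle after the fact on whichever score moved. The SAP also looks ahead to a larger randomised trial if a positive effect is seen, without saying on which score.

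**Working it through.** **Inputs.** From the SAP: four scores, .05 per test, n = 20, four time points in the power calculation, within-subject SDs of 2, 3.5 and 3.8, and a 4-unit IIEF rise. Assumed, because the documents do not give them: the means at the intermediate time points and the correlations between the changes in the four scores.

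**1. Reproduce the SAP's power.** One-way repeated measures ANOVA, df 3 and 57, noncentrality λ = 20 × Σ(mean − grand mean)² / SD². For a linear rise 18, 19.33, 20.67, 22, the grand mean is 20 and the sum of squares is 2 × 2² + 2 × 0.667² = 8.89, so λ = 177.8 / SD².

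| SD | λ | Power at .05 | SAP |
|---|---|---|---|
| 2 | 44.4 | >0.99 | >0.99 |
| 3.5 | 14.5 | 0.885 | 0.88 |
| 3.8 | 12.3 | 0.823 | 0.81 |

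The pattern 18, 20, 21, 22 gives 0.880 and 0.816 at the two larger SDs. The stated figures are thus those of one IIEF test at .05. (The SAP's table prints 18 to 20, a 2-unit rise. A linear 2-unit rise gives only 0.78, 0.31 and 0.26. That is a separate matter and does not affect this point.)

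**2. Error across the four scores when nothing changes.**
- Independent scores: 1 − 0.95⁴ = 1 − 0.8145 = 18.5%.
- Bound under any dependence: 4 × 0.05 = 20%.
- Equal correlation between change scores, simulated as four paired t-tests with n = 20 (100,000 runs): 17.5% at 0.3, 15.7% at 0.5, 13.4% at 0.7 and 9.6% at 0.9.
- Favourable direction only, two time points, independent scores: 1 − 0.975⁴ = 9.6%, against 2.5% for one test.

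The independence figure and the bound need only that each test has level .05, so they hold whether there are two time points or four. The percentage-change models are not counted and would add further unadjusted tests.

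**3. What the existing Bonferroni step does.** With m post-treatment values it tests each at .05/m, within one score, after that score's TIME effect is already significant. The four TIME tests stay at .05 each whatever m is, so the figures in step 2 are unchanged.

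**4. Cost of adjusting across scores.** Holm's first step uses .05/4 = .0125. With four tests at that level the error is 1 − 0.9875⁴ = 4.9% if independent, and at most 5%. IIEF power on the linear pattern of step 1 becomes 0.735 at SD 3.5 (from 0.885) and 0.639 at SD 3.8 (from 0.823). It stays above 0.99 at SD 2.

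**The case against.** The best defence is the setting. This is a small pilot, the protocol calls it a phase I study of safety, and its data are meant to inform the power of later studies. Strict family-wise control is often not asked of such work. That argument would be enough if the SAP were descriptive, as protocol section 5c is. It weakens once the SAP declares a primary endpoint and a significance threshold. It does support treating this as a repair of wording rather than a fatal flaw, and it makes an exploratory label an acceptable answer.

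Four stronger readings are tempting, and the documents do not support them:
- **That one significant score is the success rule, or triggers the next trial.** The word joining the four scores may simply mean that each is tested. The SAP says only that a larger trial might be considered after a measurable positive effect, and does not tie that to P<.05. What is established is the absence of a rule.
- **That 18.5% is the actual rate or a ceiling.** It is the independence value. The ceiling is 20%, and scores reported by the same men are probably positively correlated, which lowers the figure.
- **That the time-point Bonferroni is pointless.** It would be if week 4 is the only post-treatment assessment, as the protocol schedules. The SAP's power text has four time points, under which it has a purpose. The conflict is unresolved, so the point made here is only that this step does not act across scores.
- **That EHS and TSS were deliberately left without a relevance threshold.** The sentence giving the 4-unit thresholds names EDITS twice and may contain a slip.

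**Conclusion.** The point stands. As written, the plan has four co-equal primary tests at .05 and nothing that controls error across them. The chance of at least one false significant score is 18.5% under independence, bounded at 20%, and about 10% to 17% if the change scores correlate at 0.9 down to 0.3. Those correlations are assumed. Even at 0.9 the rate is nearly twice the nominal 5%. It is worth correcting, because the change is cheap and the SAP attaches significance language to these tests. It does not show that any particular claim was or will be made on a single score.

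**What to change.** In the SAP's analysis paragraphs, name one score for the single formal test at .05, and report the other three as mean change with 95% CI and no claim of significance. IIEF is the natural candidate because it is the only score the SAP sizes, and its power is then unchanged. Two conditions apply:
- State that a formal IIEF test departs from protocol section 5a and 5b, where satisfaction is primary and erectile response secondary, or reconcile the two documents.
- The SAP is written partly in the past tense. If the data have already been analysed, disclose the choice of score as post hoc. Alternatively, label all four tests exploratory, which fits section 5c and avoids choosing a score.

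If all four scores are to remain formal, apply Holm across the four TIME tests. Keep the time-point Bonferroni if there is more than one post-treatment visit, and say how many there are. Restate the power: at Holm's first step IIEF falls from about 0.89 to 0.74 (SD 3.5) and from 0.82 to 0.64 (SD 3.8), both below the 80% the SAP used as its floor.

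The single-test and exploratory options cost only wording. Holm costs about 15 to 18 points of first-step IIEF power at the two larger SDs.

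### The follow-up paired t-tests cannot show when a rise of at least 4 points is first detected: they test for any change, and only one post-treatment assessment is documented

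*SAP*

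**What the plan says.** The SAP's analysis paragraph begins with a single comparison: "Pre-treatment IIEF, EHS, EDITS, and TSS scores was planning to be compared to post-treatment scores at 4 weeks". Its primary test is for any change: "The primary endpoint was the TIME effect, i.e. to test for a change from pre-treatment value of IIEF, EHS, EDITS, or TSS". The clinical threshold follows: "The minimum change considered clinically relevant was an increase in IIEF and EDITS of 4 units and EDITS of 4 units". That sentence names EDITS twice, so it is unclear which scores carry a 4-unit threshold.

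If TIME is significant, paired t-tests compare pre-treatment with each post-treatment value, with a Bonferroni adjustment, "to determine the time at which an increase in IIEF and EDITS of at least 4 points can first be detected". The only decision criterion in the SAP is P<.05.

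The SAP's power paragraph uses a different schedule: "The table below shows power to detect a 4 unit increase in IIEF with 20 patients evaluated at 4 time points". Protocol section 2 (Study Procedures) has two clinic visits, with the questionnaires completed at baseline and at week 4. Neither document says when two further assessments would take place.

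Protocol section 5 (Study Statistics) is more modest: "Descriptive statistics will be performed based on pre-treatment and post-treatment responses to validated sexual function questionnaires".

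**The concern.** There are two mismatches between the follow-up step and its stated purpose.

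1. **Test and question.** A pre/post paired t-test with no stated null value tests a mean change of zero. Rejecting zero is evidence of some change. It is not evidence that the change is at least 4 unless the lower confidence limit also reaches 4.
2. **Schedule and question.** Finding the earliest time of detection needs several post-treatment times. The documented schedule has one.

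At stake is the only yardstick of clinical relevance in the SAP. If the step is applied as worded, a significant result with an observed mean rise of 2 or 3 IIEF points could be described as reaching the 4-point threshold.

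**Working it through.** **Inputs.** From the SAP power paragraph: n = 20, alpha = 0.05 (taken as two-sided), IIEF within-subject SD 2 / 3.5 / 3.8, target rise 4. Triplets below follow that SD order. No SD is given for EDITS, so nothing can be computed for it.

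**Reproducing the SAP's power.** Treat the SD as the residual within-subject SD and use a noncentral F for TIME with 4 time points: df 3 and 57, lambda = n × Σ(mean_t − grand mean)² / SD².
- Means rising linearly from 18 to 22: Σ = 8.89, lambda = 177.8/SD² = 44.4 / 14.5 / 12.3, power >0.99 / 0.885 / 0.823.
- Means 18, 20, 21, 22: >0.99 / 0.880 / 0.816.
- SAP: >0.99 / 0.88 / 0.81.

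So the stated power agrees to within 2 percentage points with a test of zero change sized for a 4-unit rise. The means printed in the table (18 and 20) are only 2 apart; a linear 18-to-20 pattern gives 0.78 / 0.31 / 0.26. The reproduction is not unique, because the middle means and the autocorrelation are not given. Reading the SD as a total SD with autocorrelation 0.7, two time points and means 18 and 20 gives >0.99 / 0.88 / 0.82.

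**Observed rise needed for P<.05 against zero.**
- SD of change = √2 × SD = 2.83 / 4.95 / 5.37
- SE = SD of change / √20 = 0.632 / 1.107 / 1.202
- One comparison, t(0.975, 19) = 2.093: 1.32 / 2.32 / 2.52
- Three comparisons, alpha 0.05/3, t = 2.625: 1.66 / 2.91 / 3.15

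All are below 4. For the one-comparison threshold to reach 4, the within-subject SD would have to be 4/2.093 × √20/√2 = 6.04; for three comparisons, 4/2.625 × √20/√2 = 4.82. Both exceed the largest SD in the SAP.

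**Sensitivity to the reading of the SD.** If it is a total SD with assumed autocorrelation 0.3 / 0.5 / 0.7, the SD 3.5 threshold is 2.32 × √(1 − rho) = 1.94 / 1.64 / 1.27, further below 4.

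**Example.** An observed rise of 3 gives a 95% CI of 1.68 to 4.32 / 0.68 to 5.32 / 0.48 to 5.52. All three exclude 0 and include 4.

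**How often this would arise (one comparison).** If the true rise is 2, the test is significant in 85% / 40% / 35% of trials (noncentral t). Among those, 99.9% / 91% / 86% have an observed mean below 4 (simulation, 1,000,000 runs).

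**Schedule.**

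| Source | Assessments | Post-treatment comparisons per score |
|---|---|---|
| Protocol section 2 | baseline, week 4 | 1 |
| SAP analysis paragraph, first sentence | pre-treatment, 4 weeks | 1 |
| SAP power paragraph | 4 time points | 3 |

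With one comparison, the paired t-test is the two-level TIME test again (F = t²), Bonferroni divides by 1, and there is no ordering of times to examine.

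**The case against.** The null of zero is an inference; the SAP does not write it out. The verb may be loose planning language. The power paragraph also speaks of detecting a 4-unit increase, in the usual sense of a zero-null test sized for an effect of 4. The authors may also have meant a significant result with an observed mean of at least 4. Under that rule a true rise of 2 would pass in only 0.1% / 3.5% / 4.8% of trials, and a true rise of 3 in 6% / 18% / 20%. These readings are possible and they soften the point, but the SAP states neither, and one sentence would settle it.

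A reader might go further and infer that this step distorts what follows the pilot. The documents do not support that. The condition for a larger trial is "Should a measurable positive effect be noted, a more extensive randomized, placebo controlled, blinded and possibly multi-institutional trial be considered", which a test against zero suits and which does not mention 4 points. On future planning the protocol says "This data will be utilized to perform power analyses to generate future studies"; such analyses would draw on the observed mean and SD, which the t-test wording does not change.

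Nor is the week-4 comparison itself invalid. On the documented schedule the follow-up merely repeats a sound test of any change, and so adds no error inflation.

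Finally, this is a single-arm pilot of 20 men whose protocol primary outcome is safety, tolerability and satisfaction, with erectile response secondary. That argues for a low grade. It does not remove the mismatch.

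**Conclusion.** The point holds and is minor. As worded, the follow-up step cannot support its stated conclusion: on the SAP's IIEF SDs, significance arrives at an observed rise of 1.32 to 2.52, or 1.66 to 3.15 with three comparisons, not at 4. This holds on either schedule. On the documented schedule the step is also empty, and the four time points in the power paragraph must be reconciled with the two assessments given elsewhere.

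The consequence is confined to how the 4-point clinically relevant change is interpreted and reported. The figures assume a two-sided test against zero, all 20 men assessed, a sample SD equal to the planning SD, and the SAP's SD read as residual. Confidence is high on the schedule conflict and on what a plain paired t-test shows. It is lower on whether the authors would in fact have reported P<.05 as a rise of at least 4.

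**What to change.** - For each score, report the mean change at week 4 with its 95% CI. For IIEF and EDITS, say whether the interval excludes 0 and where 4 lies relative to it.
- Do not describe P<.05 against zero as a rise of at least 4. If the intended rule was significance plus an observed mean of at least 4, write that rule down and label it as such.
- Reconcile the number of time points. If only week 4 was assessed, delete the Bonferroni follow-up and the first-detection wording. If there were three post-treatment assessments, state their timing and give 98.3% intervals (1 − 0.05/3) at each.
- Correct the threshold sentence so that it is clear which scores have a 4-unit threshold.

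**Cost.** No new data and no new test are needed, only changes to SAP and report wording, so this can be done even though the SAP describes the analysis in the past tense. The price is a less decisive report. If the true IIEF rise is 4 and there is one comparison, the interval excludes 0 but includes 4 in about 95% / 90% / 86% of trials. A lower limit of at least 4 would need an observed rise of about 4 plus the half-width, 5.32 / 6.32 / 6.52, and occurs 2.5% of the time if the true rise is exactly 4. That is a fair account of what 20 men can show.
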